Following cannabis exposure, participants will be free to self-administer the assigned nicotine/tobacco product for that session *ad-libitum* (i.e., at their own pace) over the next 5 hours. Conventional cigarettes available for study participants will be their preferred brand of cigarettes and will be purchased by study staff from a retail tobacco outlet. For the e-cigarette study conditions, participants will be provided with the popular, commercially-available, pod-style e-cigarette called the JUUL. JUUL pods contain tobacco-flavored “e-juice” and come in 2 different nicotine concentrations or “strengths” that are designated as either a low (3%; 35mg/mL) or high (5%; 59mg/mL). All cannabis and nicotine/tobacco administration will occur in a specially ventilated room located within the BPRU designed for the administration of combusted/inhaled drug products.

Date: July 15, 2022

Principal Investigator: [name]

Application Number: IRB00220975

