We have administered smoked cannabis containing 10mg THC in a prior study (Spindle, 2018) (IRB00035394). In that study, 10mg THC produced discriminative drug effects but did not produce substantial impairment or other negative effects which is why it was selected for this study. This dose also did not produce any adverse events. Following inhalation of smoked cannabis containing 10mg THC, participants self-reported an increase in pleasant drug effects (e.g., mean peak rating of 42.4 for "pleasant drug effect", on 100-point VAS) but subjective ratings of negative effects (e.g., "anxious/nervous", "unpleasant drug effect") remained largely unchanged; 10 mg THC also did not impair cognitive or psychomotor functioning compared with placebo. In another recent study in our laboratory (IRB00101744) that included heavy cannabis users, a smoked 25 mg THC dose produced a moderate drug effect (Mean peak VAS "Drug Effect" rating = 58 of a possible 100) and no adverse events or significant impairment of cognitive function was observed.

Participants will administer nicotine *ad-libitum* in this study using their preferred brand of tobacco cigarettes or the JUUL, the most popular e-cigarette on the market today (King et al., 2018). Tobacco cigarettes and JUUL e-cigarettes will be purchased by study staff from commercial retail tobacco outlets. JUUL pods will be tobacco flavored and will contain nicotine concentrations of either 3% (35mg/mL) or 5% (59mg/mL). Since participants in this study will be regular cigarette smokers and e-cigarette users, and since they will be able to titrate their nicotine dosage during the *ad-libitum* period, we do not anticipate untoward effects from the nicotine doses we will administer. To our knowledge, there is no evidence that the simultaneous administration of nicotine and cannabis will put participants at increased risk of experiencing adverse events.

- b. Justification and safety information if FDA approved drugs will be administered for non-FDA approved indications or if doses or routes of administration or participant populations are changed.
- c. Justification and safety information if non-FDA approved drugs without an IND will be administered.

An IND application has been submitted to the FDA for the administration of cannabis in this protocol (see IRB application).

Study Statistics

Date: July 15, 2022

Principal Investigator: [name]

Application Number: IRB00220975

a. Primary outcome variable.

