Primary outcome variable is the amount of nicotine used (determined by total volume of cigarette smoke or JUUL vapor inhaled) after cannabis exposure in each session. We hypothesize that exposure to active cannabis will result in greater nicotine use compared with placebo cannabis.

b. Secondary outcome variables.

Secondary outcome variables include other nicotine use behaviors (amount self-administered and puff topography outcomes), subjective drug effect ratings, cognitive and psychomotor performance, and vital signs (HR, BP). We hypothesize that nicotine use will increase subjective drug effect ratings and decrease cognitive performance after exposure to active cannabis compared with the experimental session in which no nicotine/tobacco products are consumed. We also expect that active cannabis will increase self-reported drug effects compared with placebo cannabis.

c. Statistical plan including sample size justification and interim data analysis.

The proposed sample size of 40 study completers was estimated based on limited prior studies. One study found significant effects of transdermal nicotine and smoked cannabis on subjective drug effects with a sample size of N=20, suggesting that the proposed sample size for this study is adequate to detect interactive effects of nicotine and cannabis on subjective drug effects using a within subjects design (Penetar et al., 2005). Evaluation of pharmacodynamic drug effects using a within-subjects design reduces variability across dose administration sessions and significantly increases statistical power to detect differences on the proposed study outcomes. However, because we have a greater number of dose conditions, and because a primary outcome is amount of drug self-administration rather than self-reported drug effects, we expect the need for a greater sample size in this study.

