Initial data analyses will examine whether study completers differ from non-completers with regard to demographic or cannabis use variables. This will inform the generality of the results. We will also examine the data for missing values. When missing data are found in self-report measures we will impute scores by averaging the closest pre and post values when applicable, otherwise missing data will be treated as missing in analyses. Missing data is expected to be rare given that all assessments are conducted via computer and individual items cannot be skipped. However, it is possible that a time point could be missed due to severe drug effects. Data will be evaluated for normal distribution, skewness, kurtosis and appropriate modifications will be made for data that is not normally distributed. All hypothesis tests will be two-sided; α will be set at 0.05. Nicotine/tobacco self-administration data will be analyzed using 2-tailed t-tests comparing the consumption of each nicotine/tobacco product after active versus placebo cannabis pre-treatment. Additional planned comparisons will then be conducted to compare consumption of 3% versus 5% nicotine E-Cig use following active cannabis. Secondary analyses will be conducted using repeated-measures multiple regression to evaluate the effects of nicotine/tobacco product type (None, conventional cigarette, low dose E-Cig, and high dose E-cig) and time as within-subjects factors on subjective drug effect ratings, cardiovascular effects, craving, and cognitive performance effects during sessions in which active (10mg or 25mg THC) cannabis was administered. If sufficient variability in pre-study cannabis use exists in our final study sample, we will conduct exploratory analyses comparing less frequent vs heavy (e.g. daily) cannabis users on primary and secondary outcomes.

d. Early stopping rules.

The study will be stopped if new information is learned that indicates a serious risk to study participants.

7. Risks

a. Medical risks, listing all procedures, their major and minor risks and expected frequency.

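### Total inhaled volume is labelled nicotine used; in the 3% versus 5% e-cigarette comparison it measures puffing only, and could give the wrong direction for nicotine

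*Combined protocol and SAP*

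**What the plan says.** Study Statistics, a (Primary outcome variable) gives the outcome and its measurement rule together: "amount of nicotine used (determined by total volume of cigarette smoke or JUUL vapor inhaled) after cannabis exposure in each session". The hypothesis that follows is that active cannabis leads to greater nicotine use than placebo cannabis.

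Study Statistics, c (Statistical plan) uses the word consumption, without defining it, for two analyses:

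- the main t-tests, "comparing the consumption of each nicotine/tobacco product after active versus placebo cannabis pre-treatment";
- additional planned comparisons, to "compare consumption of 3% versus 5% nicotine E-Cig use following active cannabis".

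Section 4a (Experimental Drug Exposure) describes the pods as "low (3%; 35mg/mL) or high (5%; 59mg/mL", and section 6a repeats both concentrations. Section 6a also remarks that no untoward nicotine effects are expected, partly "since they will be able to titrate their nicotine dosage during the" ad libitum period.

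Study Measures derives puff volume from a pressure sensor in the mouthpiece. Study Statistics, b lists "other nicotine use behaviors (amount self-administered and puff topography outcomes" among the secondary outcomes, and Objective 1 lists an amount consumed. Neither amount is given a unit or a method.

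**The concern.** Nicotine inhaled is volume multiplied by nicotine per mL of vapor. When the same pod strength is used in both sessions, the second factor can reasonably be treated as fixed, and volume stands in for nicotine. When two strengths are compared it cannot be taken as fixed. The plan itself calls the two conditions low dose and high dose.

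The documents define no conversion from volume to nicotine, no weighing of pods and no nicotine assay during sessions. Breath CO and cotinine appear only as eligibility checks. A catheter and blood draws are mentioned, but no nicotine measurement is attached to them. Total volume is therefore the only amount measure that is defined, and it carries the label of nicotine used.

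At stake is what may be said about pod strength. Suppose participants puff less on the 5% pod, but not by enough to offset its strength. The outcome as labelled would then report less nicotine used in the session where more was taken in.

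**Working it through.** **Inputs from the documents.** Liquid concentrations are 35 and 59 mg/mL (sections 4a and 6a agree). Their ratio is 59/35 = 1.686, close to the nominal 5/3 = 1.667, so the stated strengths are consistent. The plan has no volume-to-nicotine figure to reproduce.

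**Input assumed.** w is nicotine per mL of vapor, 5% pod relative to 3% pod. If vapor content is fully proportional to liquid strength, w = 1.686. If strength makes no difference, w = 1. The values 1.5 and 1.2 are illustrations between these two.

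**Formula.** With V3 and V5 the mean volumes in the two active-cannabis e-cigarette sessions:

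nicotine ratio (5%/3%) = (V5/V3) × w.

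Volume says less while nicotine says more when V5/V3 < 1 and (V5/V3) × w > 1, that is, when 1/w < V5/V3 < 1.

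| w | 1/w | Volume ratios with opposite directions | Largest fall in volume with nicotine still not lower |
|---|---|---|---|
| 1.686 | 35/59 = 0.593 | 0.593 to 1 | 40.7% |
| 1.5 | 0.667 | 0.667 to 1 | 33.3% |
| 1.2 | 0.833 | 0.833 to 1 | 16.7% |
| 1 | 1 | none | none |

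**One volume result under different w.** Take V5/V3 = 0.80, which reads as 20% less.

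- w = 1.686: 0.80 × 1.686 = 1.349, or 35% more nicotine.
- w = 1.5: 0.80 × 1.5 = 1.20, or 20% more.
- w = 1.2: 0.80 × 1.2 = 0.96, or 4% less, so no reversal.

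The direction changes at w = V3/V5 = 1/0.80 = 1.25.

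**By degree of titration, at w = 1.686.** With titration share c on the log scale, the volume ratio is w^(−c) and the nicotine ratio is w^(1−c).

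- No titration (c = 0): volume 1.000, nicotine 1.686. Volume shows no difference although nicotine is 69% higher.
- Half (c = 0.5): volume 0.770, nicotine 1.298. Opposite directions.
- Full (c = 1): volume 0.593, nicotine 1.000. Volume is 41% lower although nicotine is equal.
- Over-compensation (c = 1.25): volume 0.521, nicotine 0.878. Same direction.

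**The main tests.** Within one JUUL strength, active and placebo sessions use the same liquid. If nicotine per mL of vapor is also the same in both, it multiplies both volumes by one constant, and the sign and the paired t statistic do not change.

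**The case against.** The strongest reply is that the plan never draws the faulty conclusion. Its only stated hypothesis on this outcome is active versus placebo cannabis, tested within each product. No hypothesis about nicotine intake by pod strength appears. Consumption of an e-cigarette may simply mean product use. The amounts named in Objective 1 and among the secondary outcomes are listed apart from puff topography, so a different measure may be intended. The documents give no w, and a modest value such as 1.2 removes the reversal in the 0.80 example. The remark about titration in section 6a is a safety argument about what participants can do. It does not predict how far they will adjust between strengths.

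All of this stands as a limit on reach. A reader might infer that the trial will report nicotine use in the wrong direction. The documents do not support that: it needs w above 1, a volume ratio in the affected range, and a report that applies the primary outcome's label to the strength comparison. A reader might also infer that the primary test is invalid. That is not supported either, because within one strength the label does no harm if nicotine per mL of vapor is the same in both sessions.

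The reply does not remove the point. The rule in Study Statistics, a applies to each session and equates volume with nicotine used, and no other amount is defined. Across strengths that rule is safe only if w = 1, which the documents do not state either. If consumption means something else, it needs a definition before the data are analyzed.

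**Conclusion.** The point holds in a limited form. Raw volume is a valid measure of puffing at either strength, but not of nicotine used across pods of 35 and 59 mg/mL unless w = 1. For w above 1, the label gives the wrong direction whenever V5/V3 lies between 1/w and 1: 0.593 to 1 at full proportionality and 0.833 to 1 at w = 1.2. The size rests on w, which the documents do not give. It also rests on reading consumption as the primary outcome's volume, which is the natural reading but not stated.

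Only an additional planned comparison is touched. The active-versus-placebo tests remain valid as tests of volume, and nothing here bears on the sample size of 40 completers. It is still worth correcting, because it changes what the trial may conclude about pod strength and the core remedy is a change of wording.

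**What to change.** 1. Name the primary outcome total volume inhaled, and word its hypothesis and conclusions as volume for all three products.
2. Define consumption in the 3% versus 5% comparison as total volume inhaled, interpreted as puffing behavior. State that no conclusion about nicotine used across strengths will be drawn from raw volume.
3. Optionally, as a labelled sensitivity analysis only, report the mean paired difference (59/35 × V5 − V3) with its confidence interval. State that it assumes vapor nicotine proportional to liquid strength and is a relative index, not measured milligrams. Report with it the break-even w, mean V3 divided by mean V5. If w is above that value, nicotine use was higher at 5%; if below, lower. A break-even above 1.686 means nicotine was lower at 5% even under full proportionality. A break-even at or below 1 means that, for any w above 1, nicotine was higher at 5% and volume did not say otherwise.

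The break-even is preferable to requiring the same sign at a few chosen weights. A rule over 1.686 and 1.2 would leave every volume ratio from 0.593 to 0.833 undetermined, which is (0.833 − 0.593)/(1 − 0.593) = 59% of the affected range at w = 1.686. The weight 1.2 also has no source in the documents.

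Cost: a less ambitious outcome label and, if step 3 is used, one derived variable from topography data already collected, with a result that rests on an assumption. No new measurement is required.

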Objective 1 (Primary): Evaluate whether administration of THC-containing cannabis (versus placebo cannabis) subsequently influences self-administration patterns (time to first self-administration, amount consumed, puffing topography characteristics) of tobacco cigarettes or e-cigarettes.

Objective 2 (Primary): Evaluate whether administration of THC-containing cannabis (versus placebo cannabis) subsequently influences the acute effects (e.g., subjective effects) of tobacco cigarettes or e-cigarettes, nicotine withdrawal symptoms, or craving.

Objective 3 (Secondary): Evaluate whether administration of THC-containing cannabis (versus placebo cannabis) subsequently influences vital signs (e.g., heart rate, blood pressure).

Objective 4 (Secondary): Evaluate whether administration of THC-containing cannabis (versus placebo cannabis) subsequently influences cognitive performance.

3. Background (briefly describe pre-clinical and clinical data, current experience with procedures, drug or device, and any other relevant information to justify the research)

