- a. Study design, including the sequence and timing of study procedures (distinguish research procedures from those that are part of routine care).

Protocol Overview. The proposed study will be conducted at the Johns Hopkins Behavioral Pharmacology Research Unit (BPRU). All participants will be healthy adult volunteers who are regular nicotine/tobacco users, and have prior experience with cannabis use. All procedures will be for research purposes.

Participants will complete seven outpatient experimental test sessions (see table below; completed in a randomized order), under double-blind conditions, in which they will first self-administer smoked cannabis (containing 10mg THC, 25mg THC or placebo), followed by access to their preferred brand of tobacco cigarette or a commercial e-cigarette device (e.g. JUUL) containing a 3% or a 5% nicotine solution for *ad libitum* self-administration. The dose of active cannabis will be determined based on the frequency of cannabis use prior to study participation. Individuals who report using cannabis >2 times per week on average in the 3 months prior to the study will be given an active cannabis dose of 25mg THC and participants reporting cannabis use ≤2 times per week on average will be given an active cannabis dose of 10mg THC. Prior research in our lab indicates that these doses will produce a moderate drug effect across all study participants. There will also be one condition in which participants smoke active cannabis and both cigarette and e-cigarette use will be prohibited during the test session. The seven experimental sessions will consist of:

- 1) Smoked cannabis containing 10mg or 25mg THC + No nicotine/tobacco
- 2) Smoked cannabis containing 10mg or 25mg THC + *ad-libitum* use of preferred brand cigarettes

Date: July 15, 2022

Principal Investigator: [name]

Application Number: IRB00220975

- 3) Smoked cannabis containing 10mg or 25mg THC + ad-libitum use of low nicotine content E-Cig (3% nicotine JUUL)
- 4) Smoked cannabis containing 10mg or 25mg THC + ad-libitum use of high nicotine content E-Cig (5% nicotine JUUL)
- 5) Smoked placebo cannabis + ad-libitum use of preferred brand cigarettes
- 6) Smoked placebo cannabis + ad-libitum use of low nicotine content E-Cig (3% nicotine JUUL)
- 7) Smoked placebo cannabis + ad-libitum use of high nicotine content E-Cig (5% nicotine JUUL)

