The PI will follow ICH regulations (detailed in *Clinical Safety Data Management, Definitions, and Standards for Expedited Reporting*) regarding reporting of adverse events and all study deviations to the IRB and study sponsor.

d. Legal risks such as the risks that would be associated with breach of confidentiality.

Participants' names will be recorded only on the screening, informed consent, and necessary medical and payment forms. Anonymous participant identification numbers will be used on all other forms and labeling of test results. All information gathered will be kept in locked research staff offices or file cabinets. All medical information obtained will be handled in accordance with HIPAA regulations. Only research staff will have access to participant records. The limits of confidentiality (e.g. suspected child abuse or neglect, or harm to self or others) will be discussed in detail with the participants during the informed consent process. To reduce the likelihood of patient records disclosure, a Certificate of Confidentiality has been obtained for this study.

e. Financial risks to the participants.

This study does not involve patients receiving treatment; therefore, the financial risks are minimal. Participants will be fairly compensated for their time and effort in complying with the study protocol.

Date: July 15, 2022

Principal Investigator: [name]

Application Number: IRB00220975

8. Benefits

- a. Description of the probable benefits for the participant and for society.

The primary benefit of the proposed research is in the knowledge gained regarding the interactive effects of cannabis and nicotine/tobacco. The knowledge can be used to advise the treatment for disordered use of either of these drugs and provide insights into the mechanisms underlying the high rates of co-use of tobacco and cannabis. Because we anticipate relatively minor risks to these cannabis and nicotine-experienced healthy study volunteers, we feel that the proposed research has a positive risk benefit ratio.

9. Payment and Remuneration

- a. Detail compensation for participants including possible total compensation, proposed bonus, and any proposed reductions or penalties for not completing the protocol.

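### With no placebo-cannabis, no-nicotine session, 40 completers cannot show a cannabis by nicotine-versus-none interaction; only cannabis by product is estimable, and no analysis of it is planned

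*Combined protocol and SAP*

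**What the plan says.** On sample size, Study Statistics, section c, states: "The proposed sample size of 40 study completers was estimated based on limited prior studies". Its support is one earlier study: "One study found significant effects of transdermal nicotine and smoked cannabis on subjective drug effects with a sample size of N=20". From this it concludes that "the proposed sample size for this study is adequate to detect interactive effects of nicotine and cannabis on subjective drug effects" in a within-subjects design. It then adds that a larger sample than in that study is expected to be needed, because there are more conditions and a primary outcome is self-administration. No effect size, SD, within-subject correlation or power is given. On testing: "All hypothesis tests will be two-sided; α will be set at 0.05".

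On design, the Protocol Overview (section 4a) states: "Participants will complete seven outpatient experimental test sessions". Only the first of the seven withholds nicotine: "Smoked cannabis containing 10mg or 25mg THC + No nicotine/tobacco". The other six cross active and placebo cannabis with preferred-brand cigarettes, the 3% e-cigarette and the 5% e-cigarette.

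On analysis, section c compares consumption of each product after active versus placebo cannabis by t-tests. Subjective ratings, cardiovascular effects, craving and cognition go into a repeated-measures regression on product type (four levels, including none) and time, restricted to active-cannabis sessions.

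On purpose, Objective 2 asks whether THC versus placebo influences the acute effects of "tobacco cigarettes or e-cigarettes, nicotine withdrawal symptoms, or craving". The Benefits section promises "knowledge gained regarding the interactive effects of cannabis and nicotine/tobacco".

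**The concern.** An interaction of cannabis with nicotine use is a difference of differences: nicotine versus none after active cannabis, minus nicotine versus none after placebo cannabis. The second difference is never observed. If ratings after active cannabis are higher with a product than without, the cause may be nicotine acting on its own or nicotine and THC potentiating each other, and the data cannot distinguish the two. The Abstract's stated purpose is to learn how far cannabis intoxication enhances nicotine product effects, so the distinction matters.

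The sample-size text therefore claims a property that, for nicotine versus none, the design does not have. The interaction that the design does support, cannabis by product, has no planned analysis for the subjective, cardiovascular, craving and cognitive outcomes.

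**Working it through.** **1. The plan's own figure.** N = 40 cannot be reproduced, because section c gives no effect size, SD, correlation or power. The one anchor is a study with N = 20 that reached significance. According to the Background, it applied a nicotine patch four hours before cannabis; here nicotine is self-administered after cannabis, so the analogy is loose.

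**2. The cells (section 4a).**

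| | None | Cigarette | 3% e-cig | 5% e-cig |
|---|---|---|---|---|
| Active cannabis | yes | yes | yes | yes |
| Placebo cannabis | **absent** | yes | yes | yes |

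**3. Estimability.** Let m be the mean for placebo with none, a the cannabis effect without nicotine, b_p the effect of product p under placebo, and g_p the interaction for product p. The seven observable means are:

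- active, none: m + a
- placebo, product p: m + b_p (three means)
- active, product p: m + a + b_p + g_p (three means)

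This gives 8 parameters and 7 means. Replace m by m + δ, a by a − δ, each b_p by b_p − δ and each g_p by g_p + δ. All seven means are unchanged for any δ:

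- (m + δ) + (a − δ) = m + a
- (m + δ) + (b_p − δ) = m + b_p
- (m + δ) + (a − δ) + (b_p − δ) + (g_p + δ) = m + a + b_p + g_p

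The g_p are therefore determined only up to a common constant. A numerical check agrees: the design matrix has rank 7 of 8 columns, the same with 40 or 4,000 participants, and rank 8 of 8 if the missing cell is added.

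- Not estimable: cannabis by (cigarette, 3%, 5% or any nicotine) versus none; nicotine versus none under placebo; active versus placebo without nicotine.
- Estimable: g_p − g_q, that is cannabis by concentration (5% versus 3%) and cannabis by product type; active versus placebo within each product; each product versus none within active cannabis.

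Change from session baseline does not replace the missing cell unless the change under placebo without nicotine is assumed known. Each session starts with a standardised cigarette about an hour before cannabis, so assuming no change in craving over the following hours would be hard to defend.

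**4. What n = 40 can detect.** Paired t-test, two-sided α = 0.05, 80% power, noncentral t with 39 degrees of freedom: the standardised contrast (mean divided by SD of the per-person contrast) is 0.454. The normal approximation, (1.960 + 0.842)/√40 = 0.443, agrees closely. At 90% power the figure is 0.526. Power at n = 40 over an assumed range of effects, none of which is in the documents:

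| Standardised contrast | 0.2 | 0.3 | 0.4 | 0.5 | 0.6 |
|---|---|---|---|---|---|
| Power | 23% | 46% | 69% | 87% | 96% |

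**5. Cannabis by product.** Let D_p be a person's active-minus-placebo difference for product p, with SD σ_D. With equal variances and independent session errors the D_p are uncorrelated:

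- two products: Var(D_p − D_q) = 2σ_D², so the detectable effect is 0.454 × √2 = 0.642 σ_D
- cigarette versus the mean of the e-cigarettes: Var = σ_D²(1 + 1/2) = 1.5σ_D², so it is 0.454 × √1.5 = 0.556 σ_D

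If people differ in their response to cannabis, the D_p share a correlation ρ and both variances are multiplied by (1 − ρ). At an assumed ρ = 0.5 the figures become 0.454 × √1 = 0.454 and 0.454 × √0.75 = 0.393. The documents give no ρ. A 2-degree-of-freedom omnibus test would have a different threshold again.

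**The case against.** The strongest reply is that the plan does not commit itself to the interaction it cannot estimate. The secondary hypothesis on nicotine is worded as a comparison with the no-product session after active cannabis, and the regression is limited to active sessions. That is a conditional effect, and it is estimable. A reader might infer that the plan will report this effect as an interaction; its wording does not say so. What remains is that the sample-size and Benefits text both speak of interactive effects, with nothing to stop the conditional effect being read that way.

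It would also be too strong to say that no nicotine-cannabis interaction is estimable. Cannabis by concentration and cannabis by product type are, and the Background names both as questions. The reply fails at the next step, because the planned regression has no cannabis factor and so tests neither.

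A reader might further conclude that Objective 2 fails on withdrawal, since product is withheld only under active cannabis. Objective 2 does not specify withdrawal during deprivation, and active-versus-placebo craving contrasts exist in all three product conditions. The tobacco-specific scale asks about the product used, so an empty session would add nothing to it.

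Finally, 40 is twice the cited 20, section c itself argues for a larger sample, and leaving out an eighth session is a defensible choice. All of that stands. It does not make the missing interaction estimable.

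**Conclusion.** The point holds in a limited form. For general drug-effect ratings, vital signs, cognition and craving, the interaction of cannabis with nicotine versus none is not estimable at any N. This follows from the list of sessions and needs no assumption about variances. The estimable interaction, cannabis by product over the six product sessions, is not in the planned analysis of these outcomes.

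The detectable sizes at n = 40 do rest on assumptions. The 0.45 is in units of the contrast's own SD. The 0.64 and 0.56 require equal variances and independent session errors, and would fall if responses to cannabis are correlated across products. Intake is ad libitum, so even cannabis by concentration concerns access to a product and not a fixed nicotine dose.

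A reader should not take this as a flaw in the primary outcome. Consumption after active versus placebo cannabis is compared within each product and does not use the missing cell. Severity is moderate: a stated property should be withdrawn and an analysis added, with no change to the design.

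**What to change.** 1. In Study Statistics, section c, replace the adequacy sentence with what 40 completers can detect at 80% power and two-sided 0.05: a standardised paired contrast of about 0.45; and for cannabis by product, in SDs of a simple paired difference, about 0.64 for two products or 0.56 for cigarette versus the mean of the two e-cigarettes. State the assumptions of equal variances and independent session errors.
2. In the same section, add a cannabis by product (by time) model over the six product sessions for the subjective, craving, cardiovascular and cognitive outcomes. It would also supply the THC-versus-placebo contrasts that Objectives 2 to 4 ask for, which the active-only regression cannot.
3. State that product versus none is a nicotine effect conditional on active cannabis and cannot be read as potentiation. In the sample-size and Benefits text, reserve the term interactive effects for cannabis by product.
4. State that THC-versus-placebo conclusions on craving and withdrawal apply to sessions with ad libitum product access.

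The cost is wording, one further model on data already being collected, and narrower claims. Neither an eighth session nor a larger sample is needed.
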